1.3 Study Sites

This study will take place within the Nouna Health and Demographic Surveillance Site (HDSS). The HDSS covers an area of 1,775 km², covering 103,576 individuals living in 58 villages as well as the town of Nouna. For **Objective 1**, we will include 20 villages served by 6 health centers: Bourasso, Sikoro, Labarani, Lekuy, Nokuy Bobo, and Kodougou in the southeast of the HDSS. For **Objective 2**, we will include the villages of Dara and Kamadena in the western region of the HDSS. To avoid contamination between studies, the two study areas will not overlap.

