3.2.1 Sample Size

We will enroll 120 households into the four study arms (30/arm).

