3.2.3 Randomization

A list of potentially eligible households will be generated from the most recent census. This list will be sent to the study biostatistician ([name]), who will generate the randomization list. The randomization list will be 1:1:1:1 and will be generated without stratification or blocking.

The randomization list will contain the randomization arm and household identification number and will be transmitted to the field coordinator at CRSN.

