3.2.4 Community Eligibility

We will select two communities that have at least 120 households with 2 or more children under age 6-59 months at the most recent census. Children who are allergic to any of the study medications will not be enrolled in the study. Children who are receiving antibiotics for an ongoing disease won't be included in the study

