Antibiotic Resistance and Microbiome in Children Aged 1-59 months in Nouna, Burkina Faso

Manual of Operations and Procedures

NCT number 03187834

Version 1.1 June 2017

Centre de Recherche en Santé de Nouna

University of Heidelberg

Francis I. Proctor Foundation, University of California, San Francisco

Antibiotic resistance and Microbiome in Children Aged 6-59 months in Nouna, Burkina Faso

Statistical Analysis Plan, Version 1.0, June 15 2017

Study Overview

We will randomize 120 households containing 2 or more children aged 6-59 months to one of four study arms: 1) azithromycin, 2) amoxicillin, 3) cotrimoxazole, or 4) placebo. All children will receive 5 days of treatment. Full intervention details can be found in the Manual of Operations and Procedures. Rectal and nasopharyngeal swabs will be collected pre-treatment (baseline) and on Day 9 following the 5 days of treatment. Anthropometric indices (weight, height, and mid-upper arm circumference) will be collected at baseline and Day 35 (one month following treatment completion).

Randomization

The 120 households will be randomized in blocks of size 8 to one of the four treatment arms. In households randomized to treatment, all children aged 6-59 months of age will be treated, with the exception of one random child from within the household who will receive placebo. All children aged 6-59 months in households randomized to placebo will receive placebo. A random treated child from antibiotic arm households will be selected as the sentinel child for outcome assessment, and the untreated child from antibiotic arm households will also receive outcome assessment. Two children will be randomly selected from placebo households for outcome assessment.

Primary Outcome

We will compare diversity across arms at Day 9 and between time points. The primary outcome will be Simpson's index of alpha diversity. We will compare the mean Simpson's index between treatment arms with a t-test. All *P*-values will be calculated via permutation test.

Secondary Outcomes

As a secondary outcome, we will compare Shannon's index (L1 norm) between time points using a t-test. To compare if treatment significantly explains difference between the four treatment groups, we will compare Simpson's index (L1-norm) and Shannon's index (L2-norm) distances using PERMANOVA on bacterial reads.

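### Study Two draws on two villages known before allocation, yet neither the list nor any analysis uses village: a modest loss of precision, not bias

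*Protocol*

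**What the plan says.** Protocol section 1.3 states that for Objective 2 "we will include the villages of Dara and Kamadena in the western region of the HDSS". Section 3.2.4 gives the selection rule: "We will select two communities that have at least 120 households with 2 or more children under age 6-59 months at the most recent census". Neither section says how many households each village will supply. Section 3.2.1 sets the total at 120 households, 30 per arm.

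On allocation, Protocol section 3.2.3 says "A list of potentially eligible households will be generated from the most recent census", and then "The randomization list will be 1:1:1:1 and will be generated without stratification or blocking". The SAP, under Randomization, says "The 120 households will be randomized in blocks of size 8 to one of the four treatment arms". It names no stratification factor and does not say in what order the households are listed.

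On analysis, the SAP says "The primary outcome will be Simpson's index of alpha diversity". Arm means are compared by t-test, with P-values from permutation. PERMANOVA is by treatment. The ANCOVA for the growth measures adjusts only for the baseline value. The logistic models for stunting and acute malnutrition name no covariate. Village appears in none of these.

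**The concern.** A census-based list should carry each household's village before anyone is allocated. If village is left out of the list, arms can differ by chance in their mix of the two villages. If it is also left out of the analysis, any difference in diversity between the villages stays in the error term. With 30 households per arm and no stated power calculation, there is little reason to give up precision that can be had almost free. At stake is the width of the confidence intervals, mainly for the Day 9 comparison of Simpson's index, which has no covariate at all.

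**Working it through.** **Inputs from the documents.** 120 households, four arms, 30 per arm (Protocol 3.2.1); two villages (Protocol 1.3); no strata or blocks (Protocol 3.2.3) against blocks of eight (SAP, Randomization); an unadjusted t-test with permutation P-values (SAP, Primary Outcome).

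**Assumptions, because the documents give no figure.** An even 60/60 village split, one observation per household, and a village gap d of 0.3, 0.5 or 0.8 within-village SD.

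**1. The plan's own figures.** 120/4 = 30 per arm and 120/8 = 15 full blocks, so the counts agree. There is no sample-size derivation to reproduce.

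**2. Chance imbalance.** The SD of the difference in village share between two arms is sqrt(2 × 0.25/30) = 0.129, or 13 percentage points. In simulation (20,000 allocations) a given pair of arms differs by 20 points or more in about 15.5% of allocations, and some pair among the four does so in about 49%. With a 30/90 split the figures are 10.6% and 36.5%. Unstratified blocks of eight give 15.6% and 49% if the villages are mixed in list order. If the blocked list runs village by village, only one block straddles the boundary and the largest gap is 2/30, about 7 points.

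**3. Effect on the contrast.** At d = 0.5 the imbalance shifts a contrast with SD 0.5 × 0.129 = 0.065, so the 95% limit is 1.96 × 0.065 = 0.127 SD. The standard error from within-village variation alone is sqrt(2/30) = 0.258. In variance terms, 0.0042/0.0667 is about 6%.

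**4. Variance share.** R² = 0.25d²/(1 + 0.25d²), and the equivalent extra households are 120/(1 − R²) − 120 = 120 × 0.25d².

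| Assumed gap d | R² | Equivalent households |
|---|---|---|
| 0 | 0% | 0 |
| 0.3 | 2.2% | 2.7 |
| 0.5 | 5.9% | 7.5 |
| 0.8 | 13.8% | 19.2 |

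The 6% in step 3 and the 6% in this table are one quantity seen from two sides and must not be added.

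**5. Power.** With 30 per arm, two-sided 5% and 80% power (all assumed), the detectable difference is about 0.72 SD. With village adjusted for and balanced, power for that difference becomes 80.8% at R² = 0.02, 82.0% at 0.05, 84.0% at 0.10 and 87.9% at 0.20. The lost degree of freedom costs at most about 0.1 point.

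**6. Validity.** Without stratification, the simulated type I error of the unadjusted t-test is 5.2%, 4.9% and 5.2% at R² = 0, 0.05 and 0.20. With stratification by village but an unadjusted test, it falls to 4.3%, 4.0% and 2.9% at R² = 0.05, 0.10 and 0.20. The list and the analysis therefore have to change together.

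**7. If an unstratified list already exists.** Arm and village are then correlated by chance. In a two-arm model this adds on average 0.129²/(60 × 0.25) = 0.0011 to 0.0667, about 1.7% of variance. That takes back most of the 2% at d = 0.3, but less than a third of the 6% at d = 0.5. Permuting within village-by-block cells is worse. With mixed villages and blocks of eight, about 25% of households fall in cells that hold only one of the two arms. Simulated power then fell from 78% to 71% at d = 0.3, and from 75% to 70% at d = 0.5.

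**The case against.** The strongest reply is that this is a preference rather than a defect. Unstratified randomisation is valid, and its standard errors and permutation P-values already allow for chance village imbalance. That stands, and step 6 confirms it. A reader might infer from the imbalance figures that the trial is biased or its error rate wrong; the documents do not support that.

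Second, the gain rests on an assumed village gap. The two villages lie in the same part of one surveillance area, and nothing in the documents shows that they differ in diversity. That also stands, and is why the result is given as a range that starts at zero.

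Third, not every contrast is affected equally. The ANCOVA's baseline adjustment already absorbs part of a stable village difference in growth, and comparisons between time points within a child cancel a constant one. The figures above apply mainly to the unadjusted Day 9 diversity comparison.

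Fourth, the SAP does not say that its blocks run across both villages. A blocked list sorted by village would come close to balance by accident. That is fair, but neither document says the list is sorted, and the analysis would still ignore village.

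**Conclusion.** The point holds as an inexpensive improvement of low weight. Village should be known before allocation and is used nowhere. The cost is about 2%, 6% or 14% of variance in the Day 9 diversity comparison at assumed gaps of 0.3, 0.5 or 0.8 SD and an even split, and nothing if the villages do not differ. At R² of 0.05 or less the gain is two power points or fewer.

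Two stronger readings should be resisted. The 0.13 SD shift at a gap of 0.5 SD is a 95% limit, not a maximum, and it is not a second harm on top of the 6%. Nor does the lack of stratification invalidate any planned test. The contradiction between the Protocol (no blocking) and the SAP (blocks of eight) is certain from the text, and it matters here because the permutation P-values depend on which scheme was used.

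**What to change.** 1. Reconcile Protocol section 3.2.3 with the SAP's Randomization paragraph on blocking, and state the list order.
2. If the list is not yet issued, stratify it by village with a block size that fits the village counts. With 60 households per village, blocks of eight give 60/8 = 7.5 blocks, while blocks of four give 15.
3. In the SAP, add village as a fixed term to the primary Simpson's index comparison, so that the effect estimate itself is adjusted, and to the ANCOVA. Add it to the logistic models only where event counts allow: it makes the odds ratio conditional on village, and fitting may suffer for a sparse outcome such as WHZ below −3.
4. Make all permutations, including those for PERMANOVA, follow the allocation actually used.
5. If an unstratified list has already been issued, put village in the primary model or permute within village. Do not permute within village-by-block cells.

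The cost is a few lines in the list generation and the SAP, and one degree of freedom. With a list already issued, expect little net gain if the villages differ by 0.3 SD or less.

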3.2.4 Community Eligibility

We will select two communities that have at least 120 households with 2 or more children under age 6-59 months at the most recent census. Children who are allergic to any of the study medications will not be enrolled in the study. Children who are receiving antibiotics for an ongoing disease won't be included in the study

3.2.5 Household Eligibility

Households will be eligible for inclusion in the study if they have 2 or more children age 6-59 months currently residing in the household.

3.2.6 Study Medication

Study medication will be procured locally for amoxicillin and co-trimoxazole. Azithromycin and placebo will be procured in the United States as they are not readily available locally, and shipped to the study site. All medications will be prepared as an oral suspension.

3.2.6.1 Dosage Information

All children will receive 5 days of treatment. Dosages will be administered once per day for all medications with the exception of amoxicillin, which will be twice per day. Dosage will be weight-based, based on the baseline weight assessment as part of anthropometry measurements, as follows:

- Azithromycin: 10 mg/kg once daily on Day 1, then 5 mg/kg once daily Days 2-5
- Amoxicillin: 25 mg/kg/day, divided into twice daily doses for Days 1-5
- Co-trimoxazole: 240 mg daily for Days 1-5
- Placebo: Once dose daily for Days 1-5

3.2.6.2 Directly Observed Treatment

All doses of study medication will be directly observed by a field worker. Study medication will be prepared on the day of administration by staff at the CRSN and will be pre-loaded into syringes with the correct dosing based on the child's weight from the baseline assessment. Each syringe will be labeled with the child's identification and household ID number. All doses of medication will be recorded electronically on the tablet.

3.2.6.3 Adverse Events Systems

All study medications are generally well-tolerated. The most common side effects of azithromycin are diarrhea, abdominal pain, and vomiting, each of which may occur in fewer than one in twenty persons who receive azithromycin. Rarer side effects include abnormal liver function tests, allergic reactions, and nervousness. Diarrhea due to *Clostridium difficile* has been reported in rare cases.

Each day, the staff member will screen all enrolled children for any adverse event. All adverse events (non-serious and severe) will be communicated to the Medical Monitor on a daily basis.

The most common side effects of amoxicillin are diarrhea, abdominal pain, and vomiting. Rash or other hypersensitivity reactions have been reported in up to 10% of patients. Diarrhea due to *Clostridium difficile* has been reported in rare cases.

The most common side effects of co-trimoxazole (sulfamethoxazole/trimethoprim) include nausea, diarrhea, and headache. Some patients may develop a rash.

During the consent process, the common adverse reactions that may occur will be explained to parents/guardians, and they will be advised to communicate any adverse events to the local health facility immediately. If, for any reason, the participant needs further care, they will be referred to the nearest health center for examination and treatment. The health facility works closely with the Nouna HDSS, and patients who are enrolled in the study will be identified based on a unique study card that will be given to each parent/guardian for each study participant. Adverse events will be reported to the study team immediately.

3.2.7 Study Schedule

| | Day 0 | Day 1-5 | Day 9 | 4 weeks after treatment completion |
|----------------|--------------|----------------|--------------|---|
| Enrollment | X | | | |
| Anthropometry | X | | | X |
| Swabs | X | | X | |
| Randomization* | X | | | |
| Treatment | | X | | |
| Outcome survey | | | X | |

*After all baseline assessments are complete

4. SPECIMEN COLLECTION PROCEDURES

4.1 Nasopharyngeal Swabs

Nasopharyngeal swabs will be collected from a random sample of 15 children per village included in Study One for assessment of antibiotic resistance and from all children in Study Two for assessment of nasopharyngeal microbiome.

The examiner will:

1. Place a pediatric flocked swab with a nylon tip through the right nostril and down the nasopharynx of each participant. Note that if the swab is not perpendicular to the frontal plane of the face, it is likely not in the inferior turbinate.
2. Once you reach the nasopharynx, rotate the swab 180° as you remove the swab from the nose.
3. Place the swab in a tube containing 1.0 mL DNA/RNA shield media by Zymo or STGG (skim milk, tryptone, glucose, and glycerin) media, cut the handle off using sterile scissors, and close the cap of the tube with the swab immersed.
4. The nasopharyngeal swab samples in STGG will initially be stored in the field at 4°C using an insulated storage bag with Fisher brand ice gel packs, and then transferred to -20°C. The nasopharyngeal swab samples in DNA/RNA shield media will be stored in ambient temperature in the field. Then transferred to a refrigerator or freezer.
5. The scissors used to cut calcium alginate swabs will be sterilized with alcohol pads or cleaned with bleach wipes between participants. When collecting specimens in DNA/RNA shield, scissors will be cleaned between participants - first with bleach wipes, and then with alcohol pads.

Do not attempt to collect the NP swab if you are not successful after **three** attempts.

Nasopharyngeal swabs will be stored in DNA/RNA shield media by Zymo or STGG media, and standard microbiologic techniques will be used to isolate *S. pneumoniae* and test for resistance to erythromycin, tetracycline, sulfa-trimethoprine, oxicillin, and clindamycin. Resistant isolates will be assessed for the most common genetic resistant determinants (*ermB* and *mefA*) using a PCR-based assay. Serotype will be assessed using a nested PCR reaction for the most common serotypes, followed by the Quellung reaction for any untyped isolates.

Materials for Swab Collection for Resistance Testing

Swabs

NP specimens will be collected using sterile, individually-wrapped pediatric flocked swabs with a plastic swab shaft (manufactured by Copan). Nasal sites will be swabbed with a sterile, Dacron polyester-tipped swab with a plastic shaft (manufactured by Fisherbrand).

Sample Tubes

All field samples for DNA testing will be collected into sterile 2.0ml microcentrifuge tubes, manufactured by Sarstedt®. (DNA-free tubes will be used for collection in DNA/RNA shield.)

Cooler Bags with Frozen Ice Packs

Insulated cooler bags will be used to carry samples to and from the field. In addition, frozen gel ice packs designed to thaw slowly will be used to maintain the temperature in the cooler bags during transport.

-80°C Freezer

A standard -80°C freezer located at the CRSN microbiology laboratory will be used for the storage and freezing of ice packs and samples. This freezer is kept in a locked room on the grounds of the CRSN, which is under 24-hour security guard supervision.

Protocol for Tubing and Handling of Samples

The tubing and handling protocol must be carefully followed in order to prevent contamination and ensure the safe transport of the samples back to the CRSN microbiology laboratory and/or to the US for processing. The person in charge of labeling, tubing, arranging, and handling the samples needs to perform this task in the most orderly and attentive manner.

1. Both hands of the tuber should be gloved at all times. The tuber's gloves only need to be changed when any potential contamination of the gloves occurs. The tuber opens the capped, hinged lid of a microcentrifuge tube, which has been labeled with the participant's random identification number.
2. The swab is inserted by the examiner into the microcentrifuge tube held by the tuber. The swab shaft should only be inserted until the swab head is fully in the tube. The tuber will cut the swab shaft with sterile scissors.
3. The tuber should screw the cap of the microcentrifuge tube tightly, flick the tube to mix the sample with the media (for tubes with DNA/RNA shield media), and place it in the sample collection box, located in the cooler bag filled with frozen ice packs. The flap of the cooler bag should be closed between each patient. The cooler bag should be in as cool a place as possible in the field, in a shaded area out of the sun.

Upon returning from the field each day, the samples in STGG will be immediately taken to a local health center and stored in a commercial -80°C freezer, reserved solely for storage of specimens and ice packs. All samples will be in sample boxes, labeled with the village name for easy future identification.

4.2 Rectal Swabs

Rectal swabs will be collected and placed into Amies transport media or Norgen Stool Preservative. The test will require that the child's parent and examiners work together to obtain a good sample. Is it important to describe the test to the parent so that they can best assist with keeping the child still during the procedure, if necessary.

In place of stool specimens, rectal swabs can be collected in the following way:

1. Put on a clean pair of gloves.

2. Partially open the fecal swab package and remove the top section of the collection vial (this can be discarded).
3. Position the child:
 - Lie the child on his/her back, hold legs in the air (it is useful to have assistance).
 - Or have the child lay on his/her stomach across the mother/guardian's lap
4. Remove the swab from the package. Take care that the cotton tip is not touched. If it is touched, throw the swab away and begin with a new one.
5. Insert the tip of the swab into the child's anus only as far as needed to contact fecal material (1-3cm) and rotate 180 degrees. The tip should be a brownish color when removed.
6. Place swab into the preservative in the collection tube. Make sure the swab is fully submerged in the liquid preservative and then break the swab off using the pre-scored breaking point.
7. Screw the cap back on the tube and make sure that it's tightened. Wrap the area where the cap meets the tube with Parafilm to ensure that the sample will not leak, and then place the tube into the appropriate sample box.
 - If the swab cannot be broken off while the tip is fully submerged in the liquid, try twirling the swab in the liquid first (to release the contents of the sample into the preservative) before breaking it off. Avoid rubbing the sample on the tip of the swab off on the side of the tube where there is no liquid.
8. Place a random number label on the collection tube.
9. Place the tube the rectal swab container.

10. **Swab storage for Genetic analysis:** Store samples at room temperature. According to the manufacturer, the preservative in the tube will preserve DNA for 5 months at room temperature (7 days for RNA), and thereafter can be frozen (-20°C or -80°C) for long-term storage.

Rectal Swab Collection for Culturing/Microbiological Testing

Swab

An individually-wrapped Copan flocked swab with a plastic shaft will be used to collect the rectal swab and then placed into a Stool Nucleic Acid Collection and Transport Tube containing Norgen Stool Preservative or Amies Transport Medium.

Sample Tube with Media

The specimen will be in a sterile Stool Nucleic Acid Collection and Transport Tube containing Norgen Stool Preservative or Amies Transport Medium with a cap that will be tightened firmly.

Quality Control Measures for Specimen Collection

Negative Field Controls

Negative field control swabs for NP and stool will be taken in each community to assess for contamination: one control swab each (NP and stool/rectal) are taken before specimen collection begins in a community; and another (NP and stool/rectal) upon completion of

specimen collection. For each negative field control, the examiner will open a new swab as described above. Wave the swab in the air, without making contact with anyone/anything. Tube the swab in media, as described above.

Duplicate swabs

Duplicate NP swabs and rectal swabs/stool specimen will be collected from two children per community.

Stool samples

Each caregiver will be supplied with a bag and plastic child's potty chair and instructed to have their child defecate in a bag and return the bag to the stool collection station. Children that cannot produce a stool within two hours will be given supplies to collect the stool at home. Caregivers will be instructed to collect stool the following morning, after which a study team member would come to their house to pick up the specimen. From a single stool specimen, we will preserve two samples: 0.5 ml of stool in 0.5 ml ethanol and 1 gram of stool in 10 ml sodium acetate-acetic acid formalin (SAF) for microscopy. Stool samples preserved in ethanol and potassium dichromate samples will be placed on ice immediately after collection and transported to a -20°C freezer by the end of the day. SAF-preserved samples will be kept at room temperature in the shade.

Supplies for stool sample collection

- Child potty
- Wooden dowls
- Digital specimen scale
- Stool specimen tube containing 10ml SAF preservative
- 2ml tubes for PCR preservation
- Applicator stick
- Alcohol wipe
- Fine permanent Marker
- Trash bag
- Gloves
- Batteries
- Sanitizing hand wipes

Laboratory methods

a. Real-time targeted PCR

DNA will be extracted from rectal swabs and stool samples using the the ZR-96 DNA Clean & Concentrator™-5 Kit (Zymo Research Corporation, Irvine, CA). DNA concentration will be measured using the Qubit 1.0 Fluorometer (Life Technologies, Carlsbad, CA) and the Qubit

dsDNA Broad Range Assay Kit (Life Technologies). Quantitative real-time polymerase chain reaction (qPCR) will be performed to for speciation and quantification of the parasite burden as previously described by Piloette et al¹⁸. Species-specific qPCR amplification will be conducted in 7 μ l volumes, containing 3.5 μ l of 2X TaqMan Fast Universal PCR Master Mix (Life Technologies), 125 nmol of each assay's respective probe, 2 μ l of template DNA at a concentration of 1 ng/ μ l, and respective concentrations of each species-specific PCR reaction developed by Pilotte et al (see Table 2). Thermocycling conditions will be as follows: an initial 2 min incubation step at 50°C, followed by a 10 min incubation at 95°C. These incubations will be followed by 40 cycles of 95°C for 15 sec for denaturation, followed by 1 min at 59°C for annealing and extension. All reactions will be conducted using the StepOne Plus Real-Time PCR System (Life Technologies).

b. Microscopy

All sodium acetate-acetic acid formalin preserved samples will be processed at the CRSN laboratory using the diethyl ether-concentration method and examined microscopy for soil-transmitted helminth eggs and larva²⁴. Briefly, the preserved specimen will be gently shaken, then filtered and centrifuged for one minute at 2000 revolutions per minute (rpm). The supernatant will be decanted and the precipitate mixed with 7 ml of 0.85% NaCl and 3 ml of diethyl ether. The whole sample will be centrifuged again for five minutes at 2000 rpm²⁴, the supernatant decanted again, and the sediment examined with a microscope at 10x and 40x magnification for helminth eggs and intestinal protozoa cysts. For helminths, the number of eggs will be counted and recorded, with a possible range of 1 up to >100 eggs. As quality control, an independent expert laboratory technician will confirm all positive slides, as well as every 10th negative specimen.

4.3 Conjunctival Photography and Clinical evaluation.

